#### **7.1.8. Additional Analysis of Adverse Events**

No additional analysis of adverse events is planned.

#### **7.2. Laboratory Evaluations**

Laboratory data collected during the study will be analyzed and summarized using both quantitative and qualitative methods. Summaries of laboratory data will be provided for the Safety Analysis Set and will include data collected up to the last dose of study drug plus 30 days. The analysis will be based on values reported in conventional units. When values are BLQ, they will be listed as such, and the imputed value will be used for the purpose of calculating summary statistics.

A by-subject listing for laboratory test results will be provided by subject ID number and visit in chronological order for hematology, serum chemistry, and urinalysis separately. Values falling outside of the relevant reference range and/or having a severity grade of 1 or higher on the Gilead Grading Scale for Severity of Adverse Events and Laboratory Abnormalities will be flagged in the data listings, as appropriate.

No inferential statistics will be generated.

### **7.2.1. Summaries of Numeric Laboratory Results**

Descriptive statistics will be provided by treatment for each laboratory test specified in the study protocol as follows:

- Baseline values
- Values at each postbaseline time point
- Change from baseline at each postbaseline time point

A baseline laboratory value will be defined as the last measurement obtained on or prior to the date/time of first dose of study drug. Change from baseline to a postbaseline visit will be defined as the visit value minus the baseline value. The mean, median, Q1, Q3, minimum, and maximum values will be displayed to the reported number of digits; SD values will be displayed to the reported number of digits plus 1.

In the case of multiple values in an analysis window, data will be selected for analysis as described in Section 3.8.3.

### **7.2.2. Graded Laboratory Values**

The Gilead Grading Scale for Severity of Adverse Events and Laboratory Abnormalities will be used to assign toxicity grades (0 to 4) to laboratory results for analysis. Grade 0 includes all values that do not meet the criteria for an abnormality of at least Grade 1. For laboratory tests with criteria for both increased and decreased levels, analyses for each direction (ie, increased, decreased) will be presented separately. If there is any lab toxicity grading scale overlapping with normal reference ranges (eg, grade 1 scale overlaps with normal reference ranges), laboratory values within normal range will not be graded.

#### **7.2.2.1. Treatment-Emergent Laboratory Abnormalities**

Treatment-emergent laboratory abnormalities are defined as values that increase at least 1 toxicity grade from baseline at any postbaseline time point, up to and including the date of last dose of study drug plus 30 days. If the relevant baseline laboratory value is missing, any abnormality of at least Grade 1 observed within the time frame specified above will be considered treatment emergent.

#### **7.2.2.2. Summaries of Laboratory Abnormalities**

Laboratory data that are categorical will be summarized using the number and percentage of subjects in the study with the given response at baseline and each scheduled postbaseline time point.

The following summary (number and percentage of subjects) for treatment-emergent laboratory abnormalities will be provided by lab test and treatment; subjects will be categorized according to the most severe postdose abnormality grade for a given lab test within a treatment:

- Treatment-emergent laboratory abnormalities
- Treatment-emergent Grade 3 and 4 laboratory abnormalities
- Treatment-emergent Grade 2, 3 and 4 laboratory abnormalities

For all summaries of laboratory abnormalities, the denominator is the number of subjects with non-missing postbaseline values up to 30 days after last dosing date.

A by-subject listing of treatment-emergent Grade 3 or 4 laboratory abnormalities will be provided by subject ID number and visit in chronological order. This listing will include all test results that were collected throughout the study for the lab test of interest, with all applicable severity grades displayed.

### **7.3. Body Weight, Height, BMI and Vital Signs**

Descriptive statistics will be provided by treatment group for body weight, BMI and vital signs as follows:

- Baseline value
- Values at each postbaseline visit
- Change from baseline at each postbaseline visit

In the case of multiple values in an analysis window, data will be selected for analysis as described in Section 3.8.3. No formal statistical testing is planned.

A by-subject listing of vital signs will be provided by subject ID number and visit in chronological order. In the same manner, a by-subject listing of body weight, height, and BMI will be provided separately.

### **7.4. Prior and Concomitant Medications**

Medications collected at screening and during the study will be coded using the current version of the Gilead-modified World Health Organization (WHO) Drug dictionary.

All prior and concomitant medications (other than per-protocol study drugs) will be provided in a by-subject listing sorted by subject ID number and administration date in chronological order.

#### **7.4.1. Antiretroviral Medications**

Any ARV medications used prior to, during, or after the study (if collected) are all recorded on the ARV eCRF. All ARV medications recorded on the ARV eCRF will be coded using the Gilead-modified World Health Organization (WHO) Drug Dictionary for ARV medication. The WHO preferred name and drug code will be attached to the clinical database. All ARV medications recorded on the ARV eCRF will be listed. No inferential statistics will be provided.

#### **7.4.2. Prior Antiretroviral Medications**

Prior ARV medications are defined as ARV medications taken on or up to 2 days prior to the first dose date of randomized study drug based on ARVs reported on ARV eCRF.

#### **7.4.3. Concomitant Non-Antiretroviral Medications**

Concomitant non-ARV medications (ie, non-ARV medications other than study drug that are taken while receiving study drug) will be coded using the WHO Drug Dictionary. The WHO preferred name and drug code will be attached to the clinical database. Use of concomitant medications will be summarized (number and percentage of subjects) by treatment group, WHO drug class and preferred name. Multiple drug use (by preferred name) will be counted only once per subject. The summary will be sorted alphabetically by drug class and then by decreasing total frequency within a class.

If the start or stop date of non-ARV medications is incomplete, the month and year (or year alone, if month is not recorded) of the start or stop date will be used to determine whether the non-ARV medications are concomitant or not. The medication is concomitant if the month and year of the start or stop (or year of the start or stop, if month is not recorded) of the medication does not meet either of the following criteria:

- The month and year of start of the medication is after the last dose date
- The month and year of stop of the medication is before the first dose date

If the start and stop date of non-ARV medications are complete, the start date is not after the last dose date and the stop date is not before the first dose date, or the non-ARV medications are marked as ongoing and start date is on or before the last dose date, the non-ARV medications are concomitant for the study.

Summaries of non-ARV concomitant medications will be provided for the safety analysis set. Subjects with any non-ARV concomitant medications will be listed. No inferential statistics will be provided.

#### **7.5. Electrocardiogram Results**

Electrocardiogram (ECG) data will not be presented in the CSR since ECGs were not assessed in this study other than as part of the screening process for potential new subjects.

## **7.6. Other Safety Measures**

A by-subject listing of subject pregnancies during the study will be provided by subject ID number. No additional safety measures are specified in the protocol.

Although not necessarily related to safety, a by-subject listing of all comments received during the study on the comments form will be provided by subject ID number, and form for which the comment applies.

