Safety: AEs and clinical laboratory tests will be collected at every visit and summarized through Day 101 or Day 157 (30 days after the last dose of GS-9620 or placebo).

The following are DLTs:

- ALT elevation defined as:
 - $ALT \geq 10 \times ULN$ **OR**
 - confirmed ALT elevation (i.e. grade shift or $2 \times$ previous value) with evidence of worsened hepatic function (e.g. total bilirubin > 2 mg/dL above Baseline, serum albumin > 1 g/dL decrease from Baseline)
- A confirmed \geq Grade 3 AE considered by the investigator to be study drug-related

- A confirmed \geq Grade 3 lab abnormality considered by the investigator to be study drug-related and clinically significant
- A persistent (≥ 72 hours) \geq Grade 2 flu-like symptom (eg pyrexia, fatigue, myalgia, arthralgia, headache, chills) considered by the investigator to be study drug-related
- A post-dose increase in plasma HIV-1 RNA that fails to resolve to < 50 copies/mL within 10 days in Cohorts 1 to 3
- A post-dose increase in plasma HIV-1 RNA that fails to resolve to < 200 copies/mL within 10 days in Cohorts 4 to 9

The Investigator will notify the SEC within 24 hours of any DLT. The SEC may unblind the treatment assignment for a subject experiencing a DLT.

Study drug dosing for a subject may be discontinued if the subject receives GS-9620 and experiences one or more DLTs considered to be related to study drug.

A Dose Cohort may be discontinued if ≥ 2 out of 6 subjects receiving GS-9620 experience one or more DLTs considered related to study drug.

Statistical Methods:

Safety:

To evaluate overall safety, the incidences of treatment-emergent AEs and treatment-emergent laboratory abnormalities will be summarized by treatment group.

The proportion of subjects in each treatment group with an AE leading to premature discontinuation of study drug and proportion of subjects with serious adverse events (SAEs) will be summarized by treatment group.

Virology:

The change in plasma HIV-1 RNA and the incidence of detectable plasma HIV-1 RNA at each visit will be summarized by treatment group.

The change in plasma HIV-1 RNA SCA from pre-dose to 2 days post-dose may be explored.

The change in cell (PBMC) associated HIV-1 RNA from pre-dose to 2 days post-dose may be explored.

The change in HIV-1 reservoir measured by cell (PBMC) associated HIV-1 DNA from pre-dose to 2 days post-dose, and in Cohorts 4 to 9 by use of secondary assays using stored PBMC samples may be explored

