6.8. Prolonged Viremia

Subjects will be considered to have prolonged viremia if they have two consecutive plasma HIV-1 RNA levels ≥ 200 copies/mL during a single dosing period.

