6.8.1. Management of Prolonged Viremia

If plasma HIV-1 RNA level is ≥ 200 copies/mL at any visit post-dose, viral load will be tested at next scheduled visit or retested within 4 days. The next dose will be withheld and only given after viral load of ≤ 200 copies/mL is achieved. The study procedure schedule will be reset relative to the next dose of study drug.

If HIV-1 RNA viral load ≥ 200 copies/mL is confirmed during a single dosing period, then this subject will be considered to have prolonged viremia and blood samples from this visit will be used for HIV-1 genotype/phenotype testing with assays corresponding to the antiretroviral medications the subject is taking.

If primary resistance mutations to the subject's existing ART regimen are identified, a new ART regimen will be configured at the discretion of the Investigator and the subject will be discontinued from the study. If the genotyping/phenotyping assay fails to provide results or no drug resistance mutations are identified, a new ART regimen may be configured at the discretion of the Investigator. Subjects who start a new ART regimen will not be allowed to receive further doses of study drug, but can be monitored for the study duration at the discretion of the study Investigator. Subjects who remain on their current ART regimen must show confirmed HIV-1 RNA levels <200 copies/mL before resuming study drug dosing at the discretion of the Investigator.

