### **6.2.2. Analysis of Secondary Efficacy Endpoints**

The full analysis set will be used for secondary efficacy endpoint analysis.

Baseline and change from baseline in plasma  $\log_{10}$  HIV-1 RNA at postbaseline visits will be summarized by treatment group using descriptive statistics. The change from baseline in plasma  $\log_{10}$  HIV-1 RNA at postbaseline visits will be analyzed in the same fashion as that of the primary efficacy endpoint.

The number and proportion of subjects with plasma HIV-1 RNA  $\geq 50$  copies/mL at any postdose timepoint (up to 10 days after each dose for Cohorts 1-3 and 7 days after each dose for Cohorts 4-6) will be summarized by treatment group and compared between each active treatment group and the pooled placebo group using a Fisher's exact test at a two-sided 0.05 significant level. The number and percentage of subjects with HIV-1 RNA in the following categories will be summarized:

- $\geq 50$  copies/mL
- $< 50$  copies/mL

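### SAP 7.6 says the protocol sets no further safety measures, but the protocol defines prolonged viremia and viremia DLTs, and the readable SAP summarises neither these nor resistance results

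*SAP*

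**What the plan says.** Protocol 6.8 defines prolonged viremia as "two consecutive plasma HIV-1 RNA levels ≥ 200 copies/mL during a single dosing period". Under 6.8.1, after a first value at that level "viral load will be tested at next scheduled visit or retested within 4 days", the next dose is withheld, and once the value is confirmed "blood samples from this visit will be used for HIV-1 genotype/phenotype testing". Consequences for ART and for further study drug follow. Separately, the safety criteria in the synopsis and Protocol 7.6.1 list as a DLT "A post-dose increase in plasma HIV-1 RNA that fails to resolve to < 200 copies/mL within 10 days in Cohorts 4 to 9", with a parallel 50 copies/mL rule for Cohorts 1 to 3.

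SAP 7.6 provides a pregnancy listing and then says "No additional safety measures are specified in the protocol". SAP 7.1.8 plans no further adverse event analysis. HIV-1 RNA appears under efficacy in three forms: the maximum log10 change from baseline (6.1), the log10 change at each visit (6.2), and the proportion of subjects with any value of at least 50 copies/mL within 10 days (Cohorts 1-3) or 7 days (Cohorts 4-6) of a dose. For the last of these, SAP 6.2.2 says "The number and percentage of subjects with HIV-1 RNA in the following categories will be summarized", and the two categories divide at 50 copies/mL. SAP 3.8.2 keeps results from unscheduled visits out of summary tables, with exceptions that do not name HIV-1 RNA retests.

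**The concern.** The drug is intended to provoke transient viremia in people whose virus is suppressed. A short, low rise is the effect being looked for. Sustained viremia, or viremia with new resistance, is the foreseeable harm of the same mechanism. The protocol recognises this: it sets a confirmation rule, a resistance test and a DLT, and eligibility requires a fully active alternative regimen in case resistance develops.

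The SAP's one count of viremic subjects does not separate the two. A subject with a single value of 55 copies/mL and a subject with two consecutive values above 200 each add one to the same numerator. Safety and tolerability are a primary objective, yet an analyst following the SAP would produce no tabulated result for a harm the protocol itself defines. The sentence in 7.6 also tells that analyst that nothing is missing.

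**Working it through.** The documents state no figure on this point, so there is none to reproduce. The check sets the texts side by side, with some arithmetic.

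1. **Which planned outputs could show prolonged viremia?**
   - Graded laboratory tables (SAP 7.2.2): no. HIV-1 RNA has no grade in Protocol Appendix 4.
   - Laboratory listing (SAP 7.2): it names hematology, chemistry and urinalysis only.
   - Count at 50 copies/mL (SAP 6.2): any single value, with no confirmation.
   - Maximum log10 change (SAP 6.1): height only. SAP 3.7 sets values below 20 to 19 copies/mL, so from that baseline log10(50/19) = 0.42 and log10(200/19) = 1.02. A high peak is visible; confirmation and resistance are not.
   - By-visit change: group summaries could partly show persistence, but they do not identify subjects.
   - Resistance results: no table or listing in the readable text.

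2. **Confirmatory retests.** Protocol 6.8.1 allows confirmation by a retest within 4 days, which may fall outside the schedule. SAP 3.8.2 then leaves it out of summary tables. SAP 6.1.3 speaks of available on-treatment data, which might admit a retest to the maximum change, but 3.8.2 does not list this as an exception.

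3. **Scheduled post-dose visits before the next dosing day** (synopsis visit schedule, end-of-study visit excluded):
   - Cohorts 1-3: 4 per dose × 6 doses = 24, mean 4.0 per dose.
   - Cohort 4: 3 each after doses 1, 5 and 10, and 1 each after the other 7. 9 + 7 = 16, mean 1.6.
   - Cohorts 5-6: 3 each after doses 1, 5 and 10, 1 after dose 2, and 2 each after the other 6. 9 + 1 + 12 = 22, mean 2.2.

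   For 7 of 10 doses in Cohort 4, a second consecutive value must come from the next dosing-day sample or a retest. Protocol 6.8 does not say which dosing period a pre-dose sample belongs to. If it belongs to the new period, scheduled samples alone can never meet the definition for those doses.

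4. **DLT timing.** Cohorts 1-3 have a visit 10 days after each dose. In Cohorts 4-6 the last scheduled sample inside 10 days is at day 7, and the next is at day 14 (for example Day 15 − Day 1). Failure to resolve within 10 days cannot be read from scheduled samples alone.

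5. **What a count would deliver.** SAP 1.2 gives six cohorts of 6 active and 2 placebo: 36 active, 12 placebo. With zero events, the upper limit of the exact two-sided 95% interval is 1 − 0.025^(1/n):
   - n = 6: 1 − 0.025^(1/6) = 0.459, or 46%.
   - n = 12: 1 − 0.025^(1/12) = 0.265, or 26%.
   - n = 36: 1 − 0.025^(1/36) = 0.097, or 9.7%.

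   The chance of seeing at least one event is 1 − (1 − p)^n. At an assumed true risk of 5% it is 26% with 6 subjects and 84% with 36. Over an assumed range of 2% to 20% it runs from 11% to 74% and from 52% to nearly 100%.

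**The case against.** The best defence is that Protocol 6.8 is a management rule and not an endpoint. Protocol section 8, where readable, plans no analysis of prolonged viremia or resistance, so SAP 7.6 can be read as referring only to planned safety analyses. That stands in part: the omission begins in the protocol. A reader might infer that the SAP dropped a promised analysis; the documents do not support that. The defence does not rescue the sentence, because the viremia DLTs are listed under the safety criteria in the synopsis and feed the SEC's cohort-suspension rule.

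A reader might also infer that viremia is reported only as a value of at least 50 copies/mL. It is not. That is the only count of subjects, but maximum and by-visit changes also carry its size.

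Nor are ART changes absent. SAP 7.4.1 lists all ARV medication, Appendix 3 flags concomitant ARVs, and SAP 4.1.2 summarises and lists reasons for stopping study drug. None of these is tied to viremia.

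Some events may also reach the adverse event tables, since Protocol 7.1.3 requires an AE when a laboratory abnormality interrupts study drug. Protocol 7.5 restricts this to abnormalities independent of the underlying condition, which leaves HIV viremia unclear. Finally, exploratory endpoints are redacted and might cover resistance.

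**Conclusion.** The point holds in a limited form. The SAP 7.6 sentence misdescribes the protocol, and the readable SAP has no summary of confirmed viremia of at least 200 copies/mL, of viremia DLTs or of resistance results. It would be too strong to say that the trial reports nothing on this harm: peak height, ARV changes and discontinuation reasons are all planned outputs, and the AE route is possible though uncertain.

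No power, sample-size or error-rate figure changes. The loss is a protocol-defined safety result, set out by treatment and linked to its consequences. Its precision would be low for each dose (46% upper limit for 0 of 6) and more useful across active groups (9.7% for 0 of 36, if pooling across doses is accepted). The conclusion assumes that the redacted text plans no such analysis, which cannot be checked.

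**What to change.** These are changes to the SAP only and alter no clinical rule.

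- Correct the sentence in SAP 7.6 so that it refers to Protocol 6.8 and to the viremia DLTs in 7.6.1.
- Add a by-treatment count, on the Safety Analysis Set, of subjects meeting the protocol's own definitions of prolonged viremia and of viremia DLT. Include unscheduled retests as a named exception to SAP 3.8.2. State which dosing period a pre-dose sample belongs to, and whether DLTs are taken from investigator reports or derived from the HIV-1 RNA series.
- Add a by-subject listing for those subjects: HIV-1 RNA series, any available genotype/phenotype results, doses withheld, ART change and study drug discontinuation.

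The cost is one table and one listing. HIV-1 RNA, ARV and dosing data are already collected. The procedures tables do not show genotype/phenotype results, so their availability should be confirmed.

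There is a downside to state with the table. The chance of observing two consecutive values depends on visit density, which differs by cohort, while placebo is pooled over cohorts. Counts should therefore be shown with the number of post-dose samples and compared with pooled placebo cautiously.

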## **7.7. Changes From Protocol-Specified Safety Analyses**

There are no deviations from the protocol-specified safety analyses.

## 8. PHARMACOKINETIC ANALYSES

### 8.1. PK Sample Collection

Plasma VES (concentrations will be collected at the following time points **for all cohorts** relative to the Dose 1 on Day 1:

- Pre-dose ( $\leq 5$  minutes prior to dosing), 0.5, 1, 2, 4, 6, 8, 10, and 12 hours post-dose at Day 1; then one sample 48 hours post dose at Day 3

Plasma VES concentrations will be collected at the following time points **for Cohort 6** relative to the Dose 4 on Day 43:

- Pre-dose ( $\leq 5$  minutes prior to dosing), 0.5, 1, 2, 4, 6, 8, 10, and 12 hours post dose at Day 43; then one sample 48 hours post-dose at Day 45.

### 8.2. PK Analyses Related to Intensive PK Sampling

VES PK parameters will be determined in subjects in the VES PK analysis set. Concentrations of VES in plasma will be determined using validated bioanalytical assays.

#### 8.2.1. Estimation of Pharmacokinetic Parameters

PK parameters will be estimated using Phoenix WinNonlin® software using standard noncompartmental methods. The linear/log trapezoidal rule will be used in conjunction with the appropriate noncompartmental model, with input values for dose level, dosing time, plasma concentration, and corresponding real-time values, based on drug dosing times whenever possible.

All predose sample times before time-zero will be converted to 0.

For area under the curve (AUC), samples BLQ of the bioanalytical assays occurring prior to the achievement of the first quantifiable concentration will be assigned a concentration value of 0 to prevent overestimation of the initial AUC. Samples that are BLQ at all other time points will be treated as missing data in WinNonlin®. The nominal time point for a key event or dosing interval ( $\tau$ ) may be used to permit direct calculation of AUC over specific time intervals. The appropriateness of this approach will be assessed by the PK scientist on a profile-by-profile basis.

Pharmacokinetic parameters such as  $AUC_{inf}$ ,  $\lambda_z$  and  $t_{1/2}$  are dependent on an accurate estimation of the terminal elimination phase of drug. The appropriateness of calculating these parameters will be evaluated upon inspection of PK data on a profile-by-profile basis by the PK scientist.

